Low birth weight	Secondary outcome	Proportion	At delivery	Birth weight < 2500 gm	Deliveries \geq 28 weeks gestational age	Withdrawn prior to delivery or < 28 weeks gestational age or no birth weight	Inferred if no birth weight but weight available with 7 days of birth
Preterm delivery	Secondary outcome	Proportion	At delivery	Gestational age < 37 weeks	Deliveries \geq 28 weeks gestational age	Withdrawn prior to delivery or < 28 weeks gestational age	None
Congenital malformation	Secondary outcome	Proportion	At delivery	Any congenital malformation documented on exam	Deliveries \geq 28 weeks gestational age	Withdrawn prior to delivery or < 28 weeks gestational age or infant unavailable for examination	None
Composite adverse birth outcome	Secondary outcome	Proportion	At delivery	Any of the following: spontaneous abortion, stillbirth, low birth weight, preterm delivery, or congenital malformation	All deliveries	Withdrawn prior to delivery	None
Symptomatic malaria during pregnancy	Secondary outcome	Incidence	Time at risk during pregnancy	Number of episodes of fever and positive blood smear by microscopy	Duration of observation from day following 1 st dose of study drugs to delivery or premature study withdrawal	None	None
Parasitemia during pregnancy detected by LAMP	Secondary outcome	Proportion	At the time of each routine visit	Maternal blood samples with parasites detected by LAMP	Routine visits at 20, 24, 28, 32, 36, and 40 weeks of gestational age following 1 st dose of study drugs to delivery or premature study withdrawal	Missed routine visits or samples not collected	None
Maternal anemia	Secondary outcome	Proportion	At the time of each routine visit and at delivery when phlebotomy done	Hemoglobin level < 11 g/dL	Routine visits at 20,28, 36 weeks of gestational age following 1 st dose of study drugs to delivery or premature study withdrawal	Missed routine visits or sample not collected when scheduled for phlebotomy	None

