8.3 Secondary Efficacy Analyses

Secondary Outcomes: Secondary outcomes will include maternal outcomes during pregnancy and birth outcomes as listed in Table 10.

Analysis Method: A modified intention-to-treat approach will be used, including all study participants randomized to therapy with data on the secondary outcomes, regardless of whether the intervention was not given for any reason.

Secondary analyses. We will compare proportions between the study arms using the Chi-Square or Fisher's exact test for all pair-wise comparisons and presented as the risk ratio (RR) or reduction of the RR ($1 - RR \times 100\%$) if the RR is lower than 1. For repeated measures in the same study participant (maternal parasitemia and anemia during pregnancy) we will use generalized estimating equations with a log-binomial family and robust standard errors. We will compare the incidence of symptomatic

malaria during pregnancy using Poisson or negative binomial regression models. The Poisson models will include the logarithm of the follow-up time as an offset. We will translate the fitted coefficients and their confidence bounds into percentage effects with the formula $100 * [\exp(\text{coefficient}) - 1]$. This approach is closely related to exponential survival models for analyzing events per follow-up time, but is better able to adjust for violated assumptions. Testing for overdispersion in the Poisson regression can detect violations of these assumptions, and variances can be adjusted accordingly to produce valid p-values and confidence intervals. If significant deviations from required distributions in study data are detected, we will employ negative-binomial or zero-inflated negative-binomial models to account for the observed pattern of data. If necessary, multivariate analyses will be performed to adjust for potential confounders and effect modifiers. Comparisons of incidence measures will be expressed at the incidence rate ratio (IRR) or the protective efficacy ($PE = 1 - IRR \times 100\%$).

Skeleton tables for the presentation of primary and secondary efficacy outcomes are presented in Tables 11 and 12 below.

Table 11. Outcomes assessed at the time of delivery

Outcome	Treatment arm						
	3 dose SP ^a		3 dose DP		Monthly DP		
	Prevalence	Prevalence	RR (95% CI)	p-value	Prevalence	RR (95% CI)	p-value
Malaria positivity, by test							
Histopathology	n/N (%)	n/N (%)			n/N (%)		
Placental blood by microscopy	n/N (%)	n/N (%)			n/N (%)		

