Placental blood by LAMP	n/N (%)	n/N (%)			n/N (%)		
Maternal blood by microscopy	n/N (%)	n/N (%)			n/N (%)		
Maternal blood by LAMP	n/N (%)	n/N (%)			n/N (%)		
Cord blood by microscopy	n/N (%)	n/N (%)			n/N (%)		
Cord blood by LAMP	n/N (%)	n/N (%)			n/N (%)		
Birth outcomes							
Spontaneous abortion	n/N (%)	n/N (%)			n/N (%)		
Stillbirth ^b	n/N (%)	n/N (%)			n/N (%)		
Low birth weight ^b	n/N (%)	n/N (%)			n/N (%)		
Preterm delivery ^b	n/N (%)	n/N (%)			n/N (%)		
Congenital anomaly ^b	n/N (%)	n/N (%)			n/N (%)		
Composite adverse birth outcome	n/N (%)	n/N (%)			n/N (%)		

^a Reference group

^b Only includes those at least 28 weeks gestational age

Table 12. Longitudinal outcomes assessed during pregnancy

Outcome	Treatment arm						
	3 dose SP ^a		3 dose DP		Monthly DP		
Incidence measures	Events ^b	Events ^b	IRR (95% CI)	p-value	Events ^b	IRR (95% CI)	p-value
Symptomatic malaria	xx (x.xx)	xx (x.xx)			xx (x.xx)		
Prevalence measures	Prevalence	Prevalence	RR (95% CI)	p-value	Prevalence	RR (95% CI)	p-value
Detection of malaria parasites by LAMP							
All routine visits	n/N (%)	n/N (%)			n/N (%)		
20 weeks gestational age	n/N (%)	n/N (%)			n/N (%)		
24 weeks gestational age	n/N (%)	n/N (%)			n/N (%)		
28 weeks gestational age	n/N (%)	n/N (%)			n/N (%)		
32 weeks gestational age	n/N (%)	n/N (%)			n/N (%)		
36 weeks gestational age	n/N (%)	n/N (%)			n/N (%)		
40 weeks gestational age	n/N (%)	n/N (%)			n/N (%)		
Anemia defined as hemoglobin level < 11 g/dL							
All routine visits and delivery	n/N (%)	n/N (%)			n/N (%)		
20 weeks gestational age	n/N (%)	n/N (%)			n/N (%)		
28 weeks gestational age	n/N (%)	n/N (%)			n/N (%)		
36 weeks gestational age	n/N (%)	n/N (%)			n/N (%)		
At the time of delivery	n/N (%)	n/N (%)			n/N (%)		

^a Reference group

^b Number of events (incidence per person year at risk)

9 Safety and Tolerability Analyses

Safety and tolerability will be evaluated during the period following the 1st dose of study drug administration through the end of the observation period (6 weeks post-partum) or premature study withdrawal.

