9.3 Analytical Methods

We will test the hypothesis that pregnant women who receive IPTp with either 3 dose DP or monthly DP will have a lower incidence of adverse events and better tolerability compared to those who receive 3 doses of SP. A modified intention–to–treat approach to all will be used, including all study participants who received at least one dose of study drugs, regardless of whether subsequently the intervention was not given for any reason. We will compare the proportions of study participants with vomiting following each dose of study drugs using generalized estimating equations with a log–binomial family and robust standard errors to account for repeated measures in the same study participant. We will compare the incidence of various adverse events using Poisson or negative binomial regression models. The Poisson models will include the logarithm of the follow–up time as an offset. We will translate the fitted coefficients and their confidence bounds into percentage effects with the formula $100 \times [\exp(\text{coefficient}) - 1]$. This approach is closely related to exponential survival models for analyzing events per follow–up time, but is better able to adjust for violated assumptions. Testing for overdispersion in the Poisson regression can detect violations of these assumptions, and variances can be adjusted accordingly to produce valid p–values and confidence interval. If significant deviations from required distributions in study data are detected, we will employ negative–binomial or zero–inflated negative–binomial models to account for the observed pattern of data. Comparisons of incidence measures will be expressed at the incidence rate ratio (IRR) or the protective efficacy ($PE = 1 - IRR \times 100\%$). A skeleton table for the presentation of safety and tolerability outcomes are presented in Tables 13 below.

Table 13. Measures of safety and tolerability

Outcome	Treatment arm						
	3 dose SP ^a		3 dose DP		Monthly DP		
Prevalence measures	Prevalence	Prevalence	RR (95% CI)	p-value	Prevalence	RR (95% CI)	p-value
Vomiting following administration of study drugs							
Observed after administration of 1 st dose in clinic	n/N (%)	n/N (%)			n/N (%)		
Reported after administration of 2 nd dose at home	n/N (%)	n/N (%)			n/N (%)		
Reported after administration of 3 rd dose at home	n/N (%)	n/N (%)			n/N (%)		
Incidence measures	Events ^b	Events ^b	IRR (95% CI)	p-value	Events ^b	IRR (95% CI)	p-value

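### The zero-inflated negative-binomial fallback in SAP 8.3 and 9.3 has no rule for obtaining the incidence rate ratio, and its exponentiated count coefficient need not be that ratio

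*SAP*

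**What the plan says.** SAP 8.1 (Table 10) defines the symptomatic malaria outcome as an incidence with numerator "Number of episodes of fever and positive blood smear by microscopy", over observation time from the day after the first study dose. SAP 8.3 compares the incidence of symptomatic "malaria during pregnancy using Poisson or negative binomial regression models".

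The text of 8.3 then runs in this order:

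- Offset: "The Poisson models will include the logarithm of the follow-up time as an offset". No offset is stated for the other models.
- Conversion: "We will translate the fitted coefficients and their confidence bounds into percentage effects with the formula" 100*[exp(coefficient) - 1].
- Overdispersion: it can be tested for, and variances adjusted.
- Fallback on significant distributional deviation: "we will employ negative-binomial or zero-inflated negative-binomial models to account for the observed pattern of data".
- Reporting: "Comparisons of incidence measures will be expressed at the incidence rate ratio (IRR) or the protective efficacy".

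SAP 9.3 follows the same sequence for adverse events, including "we will employ negative–binomial or zero–inflated negative–binomial models to account for the observed pattern of data".

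Tables 12 and 13 give one IRR (95% CI) and one p-value for each DP arm against SP, beside a column footnoted "Number of events (incidence per person year at risk").

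Neither section says which predictors enter the zero part, which coefficient is reported, how the two parts combine, or how to choose between the negative binomial and zero-inflated models.

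**The concern.** Tables 12 and 13 set each IRR beside the arms' overall event rates, so a reader will take it as the ratio of those rates between randomised arms. A Poisson or negative binomial model with a log follow-up offset delivers that ratio directly as exp(treatment coefficient). A zero-inflated model with arm in both parts does not. Its count coefficient compares mean counts only among women outside the structural-zero class, and any treatment effect on membership of that class sits in a separate coefficient.

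The quantity reported could therefore depend on a distribution check made after the data are seen, for which the plan states no test, threshold or selection rule. At stake are the estimate, interval and p-value for one secondary efficacy outcome and for the adverse event incidence comparisons.

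**Working it through.** **Inputs.** From the SAP: the models, the conversion formula and the single reported IRR (8.3, 9.3, Tables 12 and 13). The SAP gives no figure to reproduce here: no inflation probabilities, no count means, and no power calculation for this outcome. All values of pi and mu below are assumptions chosen to show the range.

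**Formula.** For a zero-inflated negative binomial with structural-zero probability pi and count mean mu, E[Y] = (1 - pi)*mu. With subscript 0 for control and 1 for comparison:

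marginal IRR = [(1 - pi1)*mu1] / [(1 - pi0)*mu0] = [(1 - pi1)/(1 - pi0)] * exp(count coefficient).

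The two quantities agree only when pi1 = pi0.

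**Numbers put in (all assumed).**

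| pi0 | pi1 | mu1/mu0 = exp(count coefficient) | Marginal IRR | PE from marginal IRR | Effect from 100*[exp(coef) - 1] |
|---|---|---|---|---|---|
| 0.30 | 0.30 | 0.50 | (0.70/0.70)*0.50 = 0.50 | 50% | -50% (no error) |
| 0.30 | 0.40 | 0.80 | (0.60/0.70)*0.80 = 0.686 | 31% | -20% (attenuated) |
| 0.20 | 0.60 | 1.00 | (0.40/0.80)*1.00 = 0.50 | 50% | 0% (missed) |
| 0.30 | 0.65 | 1.00 | (0.35/0.70)*1.00 = 0.50 | 50% | 0% (missed) |
| 0.40 | 0.70 | 1.20 | (0.30/0.60)*1.20 = 0.60 | 40% | +20% (reversed) |
| 0.30 | 0.65 | 1.30 | (0.35/0.70)*1.30 = 0.65 | 35% | +30% (reversed) |

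**Check by fitting models.** Data were simulated with 20,000 women per arm, negative binomial dispersion 0.5 and varying follow-up. All models used a log follow-up offset. Entries are exp(treatment coefficient), taken from the count part for the zero-inflated fits.

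| pi0, pi1, count ratio | True IRR | Zero-inflated, arm in zero part | Zero-inflated, intercept-only zero part | Negative binomial | Poisson |
|---|---|---|---|---|---|
| 0.30, 0.30, 0.50 | 0.50 | 0.51 | 0.49 | 0.49 | 0.49 |
| 0.30, 0.65, 1.00 | 0.50 | 0.98 | 0.52 | 0.50 | 0.50 |
| 0.30, 0.65, 1.30 | 0.65 | 1.33 | 0.73 | 0.67 | 0.67 |

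**Reading.** The large discrepancy appears only when inflation differs by arm and arm is modelled in the zero part. With an intercept-only zero part, exp(count coefficient) is that model's own marginal ratio. It is modestly off in the unequal-inflation data because the model is misspecified there, but the effect is neither missed nor reversed. Poisson and plain negative binomial stay close to the true ratio in all three settings.

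**The case against.** The strongest reply is that the plan never says a zero-inflated coefficient will be printed as the IRR. The conversion formula follows the Poisson offset sentence and comes before the fallback. The closing sentence only requires an IRR or protective efficacy, and a marginal IRR derived from a zero-inflated fit would satisfy it. This stands: a reader might infer that the plan prescribes the wrong quantity, but the text supports only that it offers one conversion and none suited to this model.

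Second, the error needs several conditions together. The zero-inflated model must be chosen over the negative binomial, which is named first; arm must be in its zero part; inflation must differ by arm; and the raw count coefficient must be reported. This also stands, and it makes the problem contingent.

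Third, a reader might infer that a miss or reversal is to be expected because chemoprevention acts mainly by raising the share of women with no episode. Nothing in the SAP establishes that, and it would not carry over to adverse events in general. The reversal examples also need treatment to raise counts outside the zero class, for which the SAP offers no basis.

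Fourth, a reversed IRR would be visible beside the arm-specific rates in the same row. That helps detection, but the interval and p-value would still belong to the wrong quantity.

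**Conclusion.** The point holds as a gap in the analysis specification. Sections 8.3 and 9.3 permit a data-driven model under which the only stated conversion need not give the ratio of incidence rates between randomised arms.

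Its size depends on pi and mu, which the SAP does not give. Across the assumed values the consequence runs from none (equal inflation), through attenuation (20% reported against 31%), to a missed effect (IRR 1.00 against 0.50) or a reversed one (1.20 against 0.60). With an intercept-only zero part the bias was modest. These figures illustrate what could happen; they do not predict this trial's results.

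The point reaches symptomatic malaria, a secondary outcome, and adverse event incidence. The primary outcome is a proportion compared by chi-square or Fisher's exact test and is untouched. A reader might also infer that the interim safety boundary in SAP 6.5.2 is compromised, since it uses an adverse event rate ratio. That section names no model, so the inference is not supported. The change is worth making because it is cheap.

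**What to change.** In both 8.3 and 9.3, delete the zero-inflated option and name one model for all incidence outcomes: negative binomial regression with log follow-up time as offset (currently stated only for Poisson) and robust standard errors. Report exp(treatment coefficient) as the IRR. This fits the plan's existing intention to adjust variances for overdispersion, and it removes the data-dependent choice of model.

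If a zero-inflated fit is kept, prespecify the zero-part predictors and report the marginal IRR, [(1-pi1)/(1-pi0)]*exp(count coefficient), with a delta-method or bootstrap confidence interval.

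The cost is SAP wording only, with no change to design, data collection or sample size. The downside is a slightly less flexible fit to the distribution of counts.

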9.1 Adverse Events

An adverse event will be defined as "any untoward medical occurrence in a patient or clinical investigation subject administered a pharmaceutical product that does not necessarily have a causal relationship with this treatment" (ICH Guidelines E2A). An adverse event can further be broadly defined as any untoward deviation from baseline health, which includes:

- Worsening of conditions present at the onset of the study
- Deterioration due to the primary disease
- Intercurrent illness
- Events related or possibly related to concomitant medications

(International Centers for Tropical Disease Research Network Investigator Manual, Monitoring and Reporting Adverse Events, 2003).

At each scheduled and unscheduled visit to the clinic, study clinicians will assess patients according to a standardized case record form. A severity grading scale, based on toxicity grading scales developed by the NIH Divisions of AIDS (DAIDS) and the Division of Microbiology and Infectious Diseases (DMID) Pediatric Toxicity Tables, will be used to grade severity of all symptoms, physical exam findings, and laboratory results. All participants, regardless of treatment arm, will be assessed using the same standardized case record form. Adverse event monitoring will occur during the period when study drugs are given and up to 6 weeks following delivery. Data will be captured on the incidence of all adverse events, regardless of severity. For each adverse event identified as severity grade 3–4 or a serious adverse event (SAE), an additional adverse event report form will be completed.

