2.1 Preface

In sub-Saharan Africa approximately 25 million pregnant women are at risk of *P. falciparum* infection every year and 25% have evidence of placental infection.¹ Among pregnant women living in areas of stable transmission few infections lead to symptomatic malaria, however, infection is associated with maternal morbidity, such as anemia, and adverse birth outcomes including abortions, stillbirth, preterm delivery, low birth weight (LBW), and infant mortality.^{2,3}

In Africa the only widely available tools for the prevention of malaria in pregnancy are insecticide treated bednets (ITNs) and intermittent preventive therapy (IPTp) with sulfadoxine-pyrimethamine (SP). Older studies demonstrated the efficacy of IPTp with SP in reducing the risk of placental malaria and LBW.⁴⁻⁸ However, there are now concerns about the continued efficacy of IPTp given the spread of antifolate resistance. A 2007 review suggested that IPTp with SP remained beneficial in areas with antifolate resistance, however, this conclusion was based on communities where SP treatment failure rates in children remained at moderate levels.⁹ More recently, reports from East Africa have documented SP failure rates over 65% in children when used for treatment¹⁰ or prevention¹¹, and near saturation of common SP resistance alleles.^{12,13} In a recent study from Tanzania IPTp with SP was not associated with a decreased risk of placental malaria, maternal anemia, or LBW, and unexpectedly associated with an increased risk of fetal anemia.¹⁴ In a recent study from Uganda there was no significant difference in the risk of maternal infection, maternal anemia, and LBW for pregnant women receiving IPTp with SP plus ITNs vs. ITNs alone.¹⁵ In addition, most IPTp studies have defined placental malaria on the basis of placental blood smears, which dramatically underestimate the true prevalence of placental malaria. In summary, there are several lines of evidence suggesting that IPTp with SP is no longer effective in areas of East Africa with widespread antifolate resistance. New interventions to reduce the burden of malaria in pregnancy in this region are desperately needed.

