6.5.1 Purpose of Interim Analyses

Over the course of the trial, we will perform an interim safety analysis in addition to a final safety analysis for a total of two sequential evaluations of study safety. The interim safety analyses will compare the incidence rate ratio of significant adverse events (grade 3/4 & SAEs).

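### Malaria counts as an adverse event, so DP's protection dilutes any DP toxicity in the only interim safety test statistic; a malaria-excluded rate ratio should stand beside it

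*SAP*

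**What the plan says.** Section 9.1 quotes the ICH all-cause definition and widens it to "any untoward deviation from baseline health". Its list of examples includes intercurrent illness and "Deterioration due to the primary disease". A toxicity scale "will be used to grade severity of all symptoms, physical exam findings, and laboratory results", so fever and low haemoglobin are both gradable. Section 9.2 makes any inpatient admission serious. No section excludes malaria.

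Malaria is also an efficacy outcome. Table 10 counts symptomatic malaria as "Number of episodes of fever and positive blood smear by microscopy" and has a separate entry for anaemia.

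On the interim look, 6.5.1 says: "The interim safety analyses will compare the incidence rate ratio of significant adverse events (grade 3/4 & SAEs". Section 6.5.2 computes one standardized statistic from that ratio and compares it with ±2.51 (Table 6). There is no split by cause or by relation to study drug. For the final analysis, 9.3 hypothesises that women on DP "will have a lower incidence of adverse events and better tolerability compared to those who receive 3 doses of SP". It also allows incidence comparisons to be expressed as protective efficacy.

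**The concern.** The trial's premise is that SP is failing and DP will prevent malaria. If that is right, the SP reference arm will have more malaria episodes, malaria admissions and malarial anaemia, and all of these can enter its adverse event count. A pooled ratio then combines two opposing effects: fewer malaria events on DP, and any extra toxicity from DP. The direction is known in advance, and it is towards hiding harm from DP.

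This matters most at the interim, where the pooled ratio is the only quantity with a test and a boundary. At the end of the trial, a pooled ratio below 1 could be reported as better tolerability, or as protective efficacy, when it reflects prevented malaria.

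**Working it through.** **The plan's own figure.** Table 6 gives an interim bound of ±2.51 with alpha 0.00601. The one-sided tail beyond 2.51 is 0.00604, which agrees up to rounding of the bound. I take 2.51 as printed; whether it suits a look at the half-way point is a separate question.

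**Inputs.** The SAP gives no adverse event rates and no malaria share, so most inputs are assumptions:
- m, the malaria share of SP-arm grade 3/4 events and SAEs: assumed, 5% to 50%.
- e, the proportion of those events that DP prevents: 33%, borrowed from the placental malaria effect in Table 5 as a stand-in, and 70%, assumed.
- H, the true DP:SP rate ratio for all other events: assumed, mainly 2.0.
- SP-arm events at the interim: assumed, 25 (also 15 and 40).
- One DP arm against SP with equal person-time: assumed, since 6.5.2 does not name the pair of arms.

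**Formulas.**
- Pooled IRR = m(1 − e) + (1 − m)H.
- SE of log IRR = √(1/E_SP + 1/E_DP), with Poisson counts.
- Chance of crossing = Φ(ln IRR / SE − 2.51).

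**One case in full (m = 20%, e = 33%, H = 2, 25 SP events).**
- Pooled: IRR = 0.2 × 0.67 + 0.8 × 2 = 1.734. SE = √(1/25 + 1/43.35) = 0.251. z = 0.550/0.251 = 2.19. Chance = Φ(−0.32) = 37.5%.
- Malaria set aside: 20 SP and 40 DP events. SE = √(1/20 + 1/40) = 0.274. z = 0.693/0.274 = 2.53. Chance = Φ(0.02) = 51%.

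**Range (H = 2, 25 SP events).**

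| m | Pooled IRR, e = 33% / 70% | Chance of crossing, pooled, e = 33% / 70% | Chance, malaria set aside |
|---|---|---|---|
| 0 | 2.00 / 2.00 | 62.5% / 62.5% | 62.5% |
| 5% | 1.93 / 1.92 | 57% / 55% | 60% |
| 10% | 1.87 / 1.83 | 50% / 47% | 57% |
| 20% | 1.73 / 1.66 | 37.5% / 31% | 51% |
| 40% | 1.47 / 1.32 | 15% / 7% | 37.5% |

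At m = 20% with 15 SP events, the figures are 21% / 17% pooled against 29% set aside. With 40 SP events they are 60% / 51% against 76%.

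**When is harm fully cancelled?** Pooled IRR = 1 at m = (H − 1)/(H − 1 + e). For H = 1.5 that is 0.5/0.83 = 60% (e = 33%) or 0.5/1.2 = 42% (e = 70%). For H = 2 it is 1/1.33 = 75% or 1/1.7 = 59%.

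The set-aside column assumes perfect classification of malaria events, so it is an upper limit on the gain.

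**The case against.** The other side has strong points, and several stand.

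- **The definition is not wrong.** All-cause reporting is the quoted ICH standard, and an all-cause ratio is a legitimate measure of net harm. This stands: the ratio should be kept.
- **The final analysis does not rest on one ratio.** A reader might infer that efficacy and toxicity are mixed throughout the safety analysis. Table 13 does not support that. It has ratios for individual event types, for grade 3–4 events judged possibly drug-related, and for vomiting after each dose. This largely stands, with limits: SAEs have no relatedness row, event types with fewer than five events in total are not shown, and relatedness is a judgement.
- **The DSMB sees more than the statistic.** Under 6.5.4 it receives birth outcomes and SAEs by arm with short case descriptions, and it decides on the whole. Under 6.5.2 a crossing leads to notification and a report, not automatic stopping. So an uncrossed bound does not conceal events from the board. It stands too, but none of that material is a comparison separated by cause.
- **The malaria share may be small.** Section 2.1 says that "few infections lead to symptomatic malaria", and the SAP does not say how a malaria episode would be graded. At m = 5% the loss is only a few percentage points. Against that, 2.1 also says that "infection is associated with maternal morbidity, such as anemia", and haemoglobin is graded.
- **Excluding events by parasite status can create bias.** LAMP is highly sensitive, and positivity should differ by arm. As an assumed illustration, take 50% LAMP-positive on SP, 10% on DP and equal rates of non-malarial events. Dropping LAMP-positive events then gives a ratio of 0.90/0.50 = 1.8 with no toxicity at all. This rules out a LAMP-based exclusion, and it rules out replacing the all-cause ratio.

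**Conclusion.** The concern holds for the pooled quantities: the sole interim test statistic, and the all-grade-3–4 and all-SAE rows of Table 13. In these, protection by DP offsets toxicity by DP, in a direction that can be foreseen.

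The size cannot be taken from the SAP. If true toxicity doubles other events, the pooled ratio reads between 1.92 and 1.93 at a 5% malaria share and between 1.15 and 1.34 at 50%, for e from 70% to 33%. The effect on the interim test therefore runs from slight to serious, depending on a share that is not given.

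A reader might go further and infer that real DP harm would go undetected. The documents do not support that. The board has other material, the final analysis has rows that separate causes, and complete cancellation needs a malaria share of 42% or more in the cases above. What is missing is a planned comparison, at interim and final, that sets malaria aside.

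**What to change.** Keep the all-cause rate ratio as it is, and make these changes:

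1. In 6.5.2, 9.3 and Table 13, add a rate ratio for grade 3/4 events and SAEs that excludes malaria-attributable events. Define these before unblinding as febrile episodes with a positive blood smear, as in Table 10, and admissions for such episodes. Do not use LAMP positivity.
2. State in 6.5.2 whether the added ratio is tested against a bound or shown with a confidence interval only.
3. Add to Table 13 a row for SAEs possibly related to study drugs.
4. In 9.3, do not express an adverse event rate ratio below 1 as protective efficacy, or as better tolerability, unless the malaria-excluded row agrees.

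The cost is SAP wording, two table rows and one classification rule fixed in advance. The added row has somewhat fewer events. It still depends on smear results obtained after randomization, and malarial anaemia without a febrile smear-positive episode stays in it, so some distortion remains in each direction. That is why the two ratios should be read side by side.
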